### **Secondary objectives**

Objective 3: Investigate whether speech intelligibility in quiet is better with the study HAs than without HAs as measured by the German Freiburger test.

Objective 4: Investigate whether speech intelligibility in quiet with the study HAs is non-inferior (i.e. the same or better) compared to speech intelligibility in quiet with the subjects' own HAs as measured by the German Freiburger test.

Objective 5: Investigate how close the study hearing aids fitted with the fitting software to NAL-NL2 Targets match the postulated targets, as measured in-situ with real-ear measurements.

Objective 6: Investigate speech perception, sound localisation, satisfaction and quality of hearing perceived in real-life with the study hearing aids compared to the subjects' own hearing aids as measured by the SSQ17 questionnaire (German version)

Objective 7: Investigate outcomes and effectiveness of hearing aid usage in real-life with the study hearing aids compared to the subjects' own hearing aids as measured by the IOI-HA questionnaire (German version)

Objective 8: Investigate satisfaction in real-life with the study hearing aids compared to the subjects' own hearing aids as measured with the Satisfaction questionnaire (WSA internal questionnaire)

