#### **4.2.2 Secondary objectives**

For the **secondary objectives 3 and 4**, Speech intelligibility (SI) in quiet will be assessed with the Freiburger monosyllabic speech test where the outcome measure is percent correctly repeated words. The hypotheses related to the third and fourth objectives are:

**H0 (Objective 3)** SI(study HA) is not significantly different from SI without HAs

**H1(Objective 3)** SI(study HA) is significantly better than SI without HAs

**H0 (Objective 4)** SI(study HA) is significantly worse than SI(own HAs).

**H1(Objective 4)** There is no difference between SI(study HA) and SI(own HAs)

A significant difference means that the study HAs are inferior to own HAs, otherwise they are non-inferior.

The **secondary objective 5** will be assessed by calculating the absolute differences between the NAL-NL2 Target curves (Keidser et al 2011) realised in the Otometrics/Natus Freefit and the measured REAR/REIG curves after First Fit and after Fine-Tuning, if applicable. The expectation is that the deviation from the target curves is  $\leq$  5dB in the frequency range 0.25-4 kHz

The **secondary objective 6** will be addressed by asking the participants to rate speech understanding, localization and quality of sound in different situations as well as listening effort after having worn the hearing aids 10-14 days in real-life on a scale from 0-10 with a shortform of the SSQ questionnaire (SSQ 17 German Version, Kiessling 2011) in different situations. Mean rating will be calculated across the participants for each HA. For each domain we will test whether the ratings are significantly worse with study HAs compared to own HAs, if they are, that indicates the study hearing aids are inferior to own HAs. Otherwise, they are non-inferior.

The **secondary objective 7** will be addressed by asking the participants to rate hearing aid outcomes after having worn the hearing aids 10-14 days in real-life on a 5-point scale with IOI-HA (Cox & Alexander 2002, German Version Cox et al 2002). Mean rating will be calculated across the participants for each HA. For each question we will test whether the ratings are significantly worse with study HAs compared to own HAs, if they are, that indicates the study hearing aids are inferior to own HAs. Otherwise, they are non-inferior.

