For the **secondary objective 8**, to evaluate satisfaction, subjects are asked to rate their satisfaction with the hearing aids regarding several aspects including sound, conversations and overall satisfaction after having worn the hearing aids 10-14 days in real-life. In Marke-Trak10 survey (Picou, 2020), respondents rated their satisfaction on a 7-point scale, where 1 indicates very dissatisfied, 4 indicates neutral, and 7 indicates very satisfied. Respondents who indicated scores of 5, 6, or 7 were considered to be satisfied and satisfaction was reported as % satisfied of the study sample. In a similar manner the percentage of satisfied subjects will be calculated for the study HAs and compared to published values of (MarkeTrak10 (Picou, 2020) and EuroTrak German (2022 ), EuroTrak France (2022), EuroTrak Spain (2023) ). For each question we will test whether the proportion of satisfied subjects is significantly lower with study HAs compared to the published values (MarkeTrak/EuroTrak), if they are, that

indicates the study hearing aids are inferior the hearing aids reported on in the MarkeTrak/EuroTrak Reports. Otherwise, they are non-inferior.

In addition, mean ratings will be calculated across the participants and will be compared for the study HAs and own HAs and for each question we will test whether the ratings are significantly worse with study HAs compared to own HAs, if they are, that indicates the study hearing aids are inferior to own HAs. Otherwise, they are non-inferior.

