## 6.2 Devices & Fitting

The test will be conducted with CE-marked **PURE C&G 7IX M** devices.

Study HA are first fitted according to individual hearing loss, using released fitting software Connexx 9.11. Fitting formular for REM Measurements is NAL NL2. Fine Tuning to target will be done via AutoFit Feature in Connexx. After REM Measurements First Fit will be repeated with proprietary formula IXFit. Fine-tuning should be done as required by standard-of care (best practice) before sending the subjects to the home trial. Adding extra programs is allowed if requested by the subject (best practice). In the second lab session after the home trial and before the speech tests are performed, subjects will be asked if further fine-tuning is needed.

If the subject wishes for the use of Signia App as remote control during the Home Trial, the subjects are shown how to download the Signia App and the study HAs are coupled with the subject's own smartphone to support e.g. volume control via Signia App during the home trial.

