## 6.3 Workflow

All subjects will participate in two lab sessions as described below. Sessions should not exceed 90 min per subject. Additionally, subjects will do a home trial to rate subjective perception in relevant daily-life situations.

1 st lab trial Fit-to-Target	1 st Home Trial Study HAs	2 nd Lab Trial Speech tests	2 nd Home Trial Own HAs

• Audiometry & Anamnesis

• Fit to NAL_NL2

• Real-Ear Measurements

• ISTS @55/65/80 dB SPL

• Document Match-to Target

• New fitting to proprietary Rationale

• Listen to HAs in quiet and conversation and fine-tune as needed

	

• Duration 10-14 days

• Use HAs in daily life environments

• Option to come back for fine-tuning if needed

• At the end of home-trial fill out questionnaires:

◦ SSQ 17

◦ IOI-HA

◦ Satisfaction

◦ Basic User Needs

	

• Perform fine-tuning upon request

• Speech test in quiet (Freiburger @65 dB SPL)

◦ Unaided

◦ Study HAs

◦ Own HAs

• Speech test in noise (OLSA, SRT 80%, OL noise @65 dB SPL)

◦ Unaided

◦ Study HAs

◦ Own HAs

	

• Duration 10-14 days

• Use HAs in daily environments

• At the end of home-trial fill out questionnaires:

◦ SSQ-17

◦ IOI-HA

◦ Satisfaction

• Return questionnaires via mail

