## 7. Statistical design and analysis

### 7.1 Sample size estimation

The sample size is determined by considering the primary objective 1 and the related hypothesis expecting a mean difference in SRT between the study HA and no HA of at least 1 dB.

Speech intelligibility in noise is usually determined as a speech intelligibility threshold in dB SNR, so a difference between dependent mean values is analyzed. The data for these data are expected to be normally distributed, so a t-test is used to estimate the number of cases.

A mean difference in SRT of 1 dB measured with the Oldenburg sentence test (Wagener et al, 1999a-c), can be assumed as a typical difference in speech intelligibility to show a clinically meaningful improvement (Kollmeier et al, 2011).

The interindividual standard deviation in hearing-impaired test subjects for this method with the stationary noise associated with the test is 1.3 dB (Wagener & Brand, 2005). Assuming that dependent mean values for two comparative measurements show a high correlation (0.8), this results in an average effect size for the method (effect size  $dz$ ) of 0.77 and, with an  $\alpha$  value of 0.05 and a  $\beta$  value of 0.2 (power = 0.8), a number of cases of  $n = 16$ , calculated using the G\*Power (3.1.9.7) program of the University of Düsseldorf (Faul et al., 2007),

With an added 25% dropout risk this suggests that recruiting 20 subjects will be appropriate with respect to addressing the primary objectives and testing the related hypothesis.  $N = 20$  subjects will provide a statistical power of 0.9 when the other parameters are kept constant.

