## **10. Statement of compliance**

This non-significant risk device study will be carried out in accordance with:

- REGULATION (EU) 2017/745 OF THE EUROPEAN PARLIAMENT AND OF THE COUNCIL, MDR, Article 74 (1).
- BERUFSORDNUNG DER ÄRZTEKAMMER, BO ÄKN § 15

The protocol, informed consent form (ICF), privacy statement according to GDPR, recruitment materials, and all subject materials will be submitted to the medical ethics committee (Oldenburg University) for review and approval. Test persons who wish to discontinue the study before termination of the full study period can do so without retribution from Oldenburg Hörzentrum or WSA. Approval of the protocol, the consent form, and privacy statement must be obtained before any subject is enrolled.

Any amendment to the protocol will require review and approval by the medical ethics committee (Oldenburg University) before the changes are implemented to the study. In addition, all changes to the consent form or privacy statement will be approved; a determination will be made regarding whether a new consent needs to be obtained from subjects who provided consent using a previously approved consent form.

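### A subject who withdraws during the study-HA home trial contributes nothing to Objectives 1-4 and 6-8, and the plan does not ask early stoppers for data, which may favour the study HA

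*Combined protocol and SAP*

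**What the plan says.** The workflow table in section 6.3 gives the first lab visit to audiometry, fitting and real-ear measurement. The study-HA home trial of 10-14 days follows, with the instruction "At the end of home-trial fill out questionnaires" (SSQ17, IOI-HA, Satisfaction and Basic User Needs). Freiburger and OLSA, each unaided, with study HAs and with own HAs, are listed only under the second lab visit. Section 6.2 confirms the order: "In the second lab session after the home trial and before the speech tests are performed, subjects will be asked if further fine-tuning is needed".

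Section 4.2.2 ties the ratings for Objectives 6 and 7 to the same wear period ("after having worn the hearing aids 10-14 days in real-life") and does likewise for Objective 8 ("overall satisfaction after having worn the hearing aids 10-14 days in real-life").

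One study-HA objective is measured before any home use. Objective 5 is to "Investigate how close the study hearing aids fitted with the fitting software to NAL-NL2 Targets match the postulated targets", and the first-visit list includes "Document Match-to Target". Section 5.3.4 also has adverse events recorded throughout the study.

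Losses are expected. Section 7.1 states "With an added 25% dropout risk this suggests that recruiting 20 subjects will be appropriate", and section 10 states "Test persons who wish to discontinue the study before termination of the full study period can do so without retribution". Section 7.2 names the tests for each objective. In the text available, neither it nor any other section defines an analysis set, a method for missing data, an assessment at discontinuation, a record of reasons for stopping, or a rule for a subject who rejects the device. Section 11.3 deals with suspension of the whole study, not with individual withdrawal.

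**The concern.** Before the second lab visit the only device on trial is the study HA, and section 6.1 requires experienced users, who have their own aids to go back to. Withdrawal in this period could plausibly depend on how well the study HA suits the subject. If it does, those with the worst experience are the ones missing from both primary objectives and from all the ratings.

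The decision rule gives no protection. For the own-HA comparisons and for the published satisfaction figures, sections 4.2 and 7.2 read a non-significant deficit as non-inferiority, with no margin. Losing dissatisfied subjects raises the estimate and reduces the number analysed, and both make a non-significant result more likely.

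Objective 8 is the most exposed. Its first analysis sets a single proportion of satisfied study-HA users against external survey figures, with no within-subject pairing. A subject who rejects the device and leaves drops out of the denominator. A rating not collected at the time cannot be recovered at the analysis.

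**Working it through.** **1. The plan's own figures (section 7.1).** Inputs: dz = 0.77, alpha 0.05, power 0.80. A two-sided paired t-test (noncentral t) gives n = 16 with power 0.82, and power 0.90 at N = 20; both stated figures reproduce. The allowance is 16 × 1.25 = 20. On that arithmetic the plan can lose 20 − 16 = 4 subjects. If 25% is read as a share of those recruited, 0.25 × 20 = 5 are lost and 15 remain (two-sided power 0.79). The plan does not split losses by stage or reason.

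**2. What a withdrawal in the first home trial removes.**

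| Objective | When study-HA data are taken | Available after withdrawal in home trial 1? |
|---|---|---|
| 1-4 (OLSA, Freiburger) | Second lab visit | No |
| 5 (real-ear match) | First lab visit | Yes |
| 6-8 (SSQ17, IOI-HA, Satisfaction) | End of home trial 1 | No |
| Adverse events | Throughout | Yes, while on study |

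**3. Speech tests.** All three conditions are measured in one session, so a withdrawal loses all of them together. The bias in the mean within-subject difference is

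bias = (share lost) × (mean difference in completers − mean difference in those lost).

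Take completers at the plan's 1 dB benefit and 5 of 20 lost; the mean among those lost is assumed:

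- 1 dB: 0.25 × (1 − 1) = 0 dB
- 0.5 dB: 0.25 × (1 − 0.5) = 0.125 dB
- 0 dB: 0.25 × (1 − 0) = 0.25 dB
- −1 dB: 0.25 × (1 + 1) = 0.50 dB

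With 1 of 20 lost, the last two become 0.05 × 1 = 0.05 dB and 0.05 × 2 = 0.10 dB. The bias is zero whenever leaving is unrelated to the within-subject difference.

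**4. Proportion satisfied (Objective 8).** The documents name the published surveys but give no benchmark value, so 75%, 80% and 85% are assumptions. The exact one-sided p-value is P(X ≤ s) for X ~ Binomial(n, benchmark). Losses counted as not satisfied are added to n but not to s.

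| Assumed benchmark | Completers only | Losses counted as not satisfied | Below 0.05? |
|---|---|---|---|
| 80% | 12/15, p = 0.60 | five: 12/20, p = 0.032 | Yes |
| 80% | 12/15, p = 0.60 | four: 12/19, p = 0.068 | No |
| 80% | 13/16, p = 0.65 | four: 13/20, p = 0.087 | No |
| 80% | 15/19, p = 0.54 | one: 15/20, p = 0.37 | No |
| 85% | 12/15, p = 0.40 | three: 12/18, p = 0.042 | Yes |
| 85% | 13/15, p = 0.68 | three: 13/18, p = 0.12 | No |
| 75% | 12/15, p = 0.76 | five: 12/20, p = 0.10 | No |

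In the first row the estimate moves from 80% to 60%. The 85% row that changes starts from completers already below the benchmark (12/15 = 80%).

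**The case against.** The strongest reply is that stopping wear is not the same as leaving the study. Section 6.3 has all subjects attend both lab sessions, and nothing makes 10-14 days of wear a condition for the second. A subject who puts the device aside on day 3 but attends can still be tested in all three conditions, and nothing forbids taking a questionnaire from that subject. The plan also works against early stopping: fine-tuning visits during the home trial, extra programs on request, and an inclusion criterion of willingness to wear the HAs for two weeks. This stands. The certain loss is limited to subjects who withdraw from the study. For those who only stop wearing the device, the plan is silent, which leaves their inclusion to be decided afterwards in an unblinded study (section 9.4).

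A reader might infer that early stoppers enter no study-HA endpoint, or that the results are biased in the device's favour. The documents support neither. Objective 5 and adverse events are still captured. Bias depends on how many leave and why; the direction is plausible, not shown. It could also run the other way: Objectives 6-7 and the mean ratings in Objective 8 need own-HA forms returned by mail after the second home trial, and subjects unhappy to return to their own HAs might not send them.

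The satisfaction illustration is a worst case. The 25% is a general allowance, four subjects on the plan's own arithmetic, and the change at 80% needs five losses, all of them device rejections.

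Finally, section 4.2.2 describes the benchmark as a percentage of survey respondents. Counting non-raters as not satisfied on the study side alone makes the comparison uneven, so this belongs in a sensitivity analysis and not in the main one. This stands too.

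**Conclusion.** The point holds as a cheap improvement to data collection. A subject who withdraws during the study-HA home trial is lost to Objectives 1-4 and 6-8, and the available text asks nothing of such a subject. If withdrawal is related to dissatisfaction with the study HA, the results may favour it. For OLSA and Freiburger this requires leaving to depend on the within-subject difference; under the assumptions shown the bias is 0 to 0.50 dB at 25% loss, against the plan's 1 dB meaningful difference. For the proportion satisfied the shift is at most 20 percentage points in the example used, and it alters the conclusion only in some assumed scenarios. None of this shows that bias will occur, since neither the number of early stoppers nor their reasons can be known from the plan.

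**What to change.** **Section 6.3.** State that a subject who stops wearing the study HA early is asked to complete the SSQ17, IOI-HA and Satisfaction questionnaires at that point, and is still invited to the planned visit-2 speech tests in the randomised order. Record wear time and the reason for stopping, and say that these data are included in the analysis.

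**Section 7.2, Objective 8.** Add a sensitivity analysis in which subjects who stop because of dissatisfaction with the study HA and give no rating count as not satisfied. Keep the proportion among raters as the main analysis.

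**Cost.** A few lines of text. These subjects will have worn the device for less than 10 days, so their ratings rest on shorter experience; some will decline; and a few may need to attend visit 2 earlier than scheduled. It should not be assumed that testing can be combined with handing back the device: sections 2.3 and 9.1 cover return from the site to the sponsor and do not say how subjects return devices.

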## 7. Statistical design and analysis

### 7.1 Sample size estimation

The sample size is determined by considering the primary objective 1 and the related hypothesis expecting a mean difference in SRT between the study HA and no HA of at least 1 dB.

Speech intelligibility in noise is usually determined as a speech intelligibility threshold in dB SNR, so a difference between dependent mean values is analyzed. The data for these data are expected to be normally distributed, so a t-test is used to estimate the number of cases.

A mean difference in SRT of 1 dB measured with the Oldenburg sentence test (Wagener et al, 1999a-c), can be assumed as a typical difference in speech intelligibility to show a clinically meaningful improvement (Kollmeier et al, 2011).

The interindividual standard deviation in hearing-impaired test subjects for this method with the stationary noise associated with the test is 1.3 dB (Wagener & Brand, 2005). Assuming that dependent mean values for two comparative measurements show a high correlation (0.8), this results in an average effect size for the method (effect size  $dz$ ) of 0.77 and, with an  $\alpha$  value of 0.05 and a  $\beta$  value of 0.2 (power = 0.8), a number of cases of  $n = 16$ , calculated using the G\*Power (3.1.9.7) program of the University of Düsseldorf (Faul et al., 2007),

With an added 25% dropout risk this suggests that recruiting 20 subjects will be appropriate with respect to addressing the primary objectives and testing the related hypothesis.  $N = 20$  subjects will provide a statistical power of 0.9 when the other parameters are kept constant.

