## **7.2 Statistical analysis**

**Objectives 1 and 2** (Speech in Noise OLSA): The SRT data will be analyzed using a one-tailed paired t-test.

**Objectives 3 and 4** (Speech in Quiet Freiburger): Similarly to the OLSA Test the % correct data will be analyzed using a one-tailed paired t-test.

**Objective 5** (NAL-NL2 Targets): No statistical analysis will be performed, only descriptive statistics will be used.

**Objectives 6-7** (Questionnaires – SSQ17, IOI-HA)

Subjective rating data from real-life questionnaires will be analyzed using one-tailed paired t-tests, comparing ratings of study HA and own HA with a significance level of 0.05 to determine significance.

In addition, descriptive statistics of the SSQ 17 scores and IOI-HA scores will be reported by Hearing Aid (study or own) for each subscale and put into perspective of published data (von Gahlenz et al, 2018; Cox et al, 2013).

**Objective 8** (Questionnaire – Satisfaction)

One-sided test of proportions will be done to analyze whether the proportion of satisfied hearing aid users is significantly lower with study hearing aids than reported in the literature (MarkeTrak 10, EuroTrak). A significant effect indicates that the study hearing aids are inferior, otherwise they are non-inferior.

In addition, subjective rating data from satisfaction questionnaire will be analyzed using one-tailed paired t-tests, comparing ratings of study HA and own HA with a significance level of 0.05.

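### Section 7.1: the stated SD of 1.3 dB and correlation of 0.8 do not give dz = 0.77 (equal SDs give 1.22), and n = 16 with power 0.9 fit a two-sided test, whereas 7.2 plans a one-tailed one

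*Combined protocol and SAP*

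**What the plan says.** Section 7.1 (Sample size estimation) sizes the study on primary objective 1 alone, "expecting a mean difference in SRT between the study HA and no HA of at least 1 dB". For variability it gives a single figure: "The interindividual standard deviation in hearing-impaired test subjects for this method with the stationary noise associated with the test is 1.3 dB". The next step reads "Assuming that dependent mean values for two comparative measurements show a high correlation (0.8), this results in an average effect size" dz of 0.77. With alpha 0.05 and power 0.80, the section reports n = 16 from G*Power. It then adds 25% for dropout to reach 20 and states that 20 "subjects will provide a statistical power of 0.9 when the other parameters are kept constant". It does not say whether the calculation is one-sided or two-sided.

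Section 7.2 (Statistical analysis) plans for objectives 1 and 2: "The SRT data will be analyzed using a one-tailed paired t-test". It gives no alpha for these two objectives; 0.05 is printed there only for the questionnaire comparisons.

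**The concern.** For a paired t-test, dz is the mean difference divided by the SD of the within-subject difference. A high correlation between the two measurements makes that SD smaller than the between-subject SD and so raises dz. Here dz equals 1 dB divided by the between-subject SD itself, so the correlation of 0.8 that is offered as the reason for the result appears to have had no effect on it. The n and the power also look like two-sided results, although the planned test is one-tailed.

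This is the only sample-size justification in the plan, and it concerns a primary objective. As written, a reader cannot tell whether the design assumes an SD of the paired difference of 0.82 dB or 1.30 dB, nor which test was sized. That SD is the figure one would later compare with the observed data.

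**Working it through.** **Inputs.** From 7.1: difference 1 dB, SD 1.3 dB, correlation ρ = 0.8, alpha 0.05, target power 0.80, printed dz 0.77, printed n 16, recruited N 20, printed power 0.9 at N = 20. From 7.2: paired t-test, one-tailed. Assumption added here: equal SDs in the two conditions, because the plan gives only one SD.

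**Method.** Exact power of the paired t-test from the noncentral t distribution with n − 1 degrees of freedom and noncentrality dz·√n.

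**Step 1: reproduce the plan's n and power from its own dz.** At dz = 0.77 and alpha 0.05:

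| Test | Smallest n for power 0.80 | Power at that n | Power at n = 15 | Power at n = 16 | Power at N = 20 |
|---|---|---|---|---|---|
| Two-sided | 16 | 0.821 | 0.792 | 0.821 | 0.904 |
| One-sided | 12 | 0.803 | 0.883 | 0.902 | 0.953 |

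The printed pair (n = 16, power 0.9 at 20) is reproduced two-sided and not one-sided. A normal approximation does not give 16 either: it gives 13.2 two-sided and 10.4 one-sided.

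**Step 2: derive dz from the stated inputs.**

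- SD of the difference = SD·√(2(1 − ρ)) = 1.3·√(2 × 0.2) = 1.3 × 0.6325 = 0.822 dB.
- dz = 1/0.822 = 1.216, against the printed 0.77.

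**Step 3: find where 0.77 comes from.**

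- 1/1.3 = 0.769, so 1.3 dB has been used as the SD of the difference.
- With equal SDs of 1.3 dB, the correlation implied by dz = 0.77 is 1 − (1/0.77)²/(2 × 1.3²) = 0.501.
- To keep ρ = 0.8 with one SD at 1.3 dB and an SD of the difference of 1.3 dB, the second SD s must solve s² − 2(0.8)(1.3)s + 1.3² = 1.3². This gives s = 2.08 dB.
- If both SDs are equal and ρ = 0.8, each must be (1/0.77)/√0.4 = 2.05 dB.
- Neither 2.08 nor 2.05 dB appears in the plan.

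**Step 4: what the stated inputs would give.** At dz = 1.216 and alpha 0.05:

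| Test | Smallest n for power 0.80 | Power at that n | Power at n = 15 | Power at N = 20 |
|---|---|---|---|---|
| Two-sided | 8 | 0.838 | 0.992 | 0.9993 |
| One-sided | 6 | 0.817 | 0.998 | 0.9998 |

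**Step 5: the dropout margin.** The plan's 20 is 16 × 1.25. If 25% of 20 are lost, 15 remain. The n = 15 columns then apply: at dz = 0.77, power is 0.88 one-sided and 0.79 two-sided; at dz = 1.216 it exceeds 0.99 either way.

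**The case against.** The strongest reply is that nothing in the trial depends on this. Both discrepancies err on the safe side, and sizing two-sided before testing one-tailed is a permissible conservative choice. That stands as a limit on the weight of the point. It does not make the derivation correct, and 7.1 does not say that such a choice was made.

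Secondly, the dz result rests on equal SDs, and unaided and aided SRTs need not have the same spread. This is true, and a second SD of about 2.08 dB would rescue 0.77. But 7.1 states one SD and presents dz as the result of that SD and the correlation, so the step does not follow from what is written.

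Thirdly, a one-sided alpha of 0.025 gives the same n = 16 and power 0.90 as the two-sided calculation. Also true, but the plan prints 0.05 and nowhere 0.025.

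Finally, the sponsor should not relabel 1.3 dB as the SD of the difference merely to preserve a printed number, since 7.1 calls it interindividual and cites a source for it. That caution is fair, and the correction should start from the inputs actually entered in G*Power. A coherent version of 0.77 needs no relabelling of the source, however: an SD of 1.3 dB in each condition with a correlation of 0.5 gives an SD of the difference of 1.3 dB.

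**Conclusion.** The concern holds on both parts. With equal SDs, the stated inputs give dz = 1.22, not 0.77; the printed value corresponds to a correlation of 0.5 rather than 0.8. At the printed alpha of 0.05, n = 16 and power 0.90 at N = 20 follow from 0.77 only two-sided, while the one-tailed test in 7.2 needs 12 and has power 0.95 at 20.

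For objective 1, the only objective that 7.1 sizes, N = 20 is adequate under the planned one-tailed test at either dz, even with 15 completers (power 0.88 or higher). The one marginal case is a deliberately two-sided test at dz = 0.77 with 15 completers, where power is 0.79, just under the 0.80 target. Nothing is claimed here about objective 2. The documented basis for the sample size should be corrected; more subjects are not needed.

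**What to change.** Keep N = 20. Check what was entered in G*Power, then correct 7.1 in one of two ways:

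1. State that the SD of the paired difference is assumed to be 1.3 dB (equivalent to SDs of 1.3 dB in both conditions with correlation 0.5), remove the 0.8, and keep dz = 0.77. This is the simpler change if it matches the inputs used.
2. Keep the correlation of 0.8, state equal SDs, and give dz = 1.22, n = 6 one-sided (8 two-sided) and power above 0.99 at N = 20, with a reason for still recruiting 20.

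If unequal SDs were in fact assumed, print the second SD with its basis.

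In every case state the sidedness and alpha. Under option 1, the one-tailed test of 7.2 reads n = 12 and power 0.95 at N = 20. Alternatively, say that the sizing is deliberately two-sided, which keeps n = 16 and power 0.90, and note that 15 completers would then give 0.79.

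The cost is one or two sentences in 7.1, with no change to recruitment or analysis. The downside of option 1 is that it discloses a less favourable correlation than the one printed; option 2 leaves N = 20 needing a separate justification.

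### Section 7.1: 20 recruits cover a 20% dropout, not the stated 25%, and the quoted power of 0.9 requires all 20 to be analysed

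*Combined protocol and SAP*

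**What the plan says.** Section 7.1 sizes the trial on primary objective 1, "expecting a mean difference in SRT between the study HA and no HA of at least 1 dB". It takes an effect size dz of 0.77, alpha 0.05 and power 0.8, and obtains n = 16 from G*Power. It does not say whether alpha is one- or two-tailed.

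It then moves from 16 to the recruitment target: "With an added 25% dropout risk this suggests that recruiting 20 subjects will be appropriate with respect to addressing the primary objectives". The sentence after that gives a second power figure: N = 20 "subjects will provide a statistical power of 0.9 when the other parameters are kept constant". No power after dropout is given.

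Two other places bear on the point. Section 7.2 plans a one-tailed paired t-test for objectives 1 and 2 and names no method for missing data. The workflow in section 6.3 puts all OLSA testing (unaided, study aids, own aids) in the second lab session, after the first home trial and before the second.

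**The concern.** A dropout rate is a fraction of the people recruited. To end with n completers when a fraction d is lost, one recruits n/(1 − d). Section 7.1 appears to have used n(1 + d), which always gives too few. The number evaluable under the plan's own 25% would then fall below the plan's own 16.

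Attrition before the second lab session acts directly on the primary endpoint. A subject who leaves during the first home trial has no SRT in any condition and cannot enter the paired test. The power quoted for N = 20 makes no allowance for such losses and does not say so, so a reader could take 0.9 as the power expected with dropout already allowed for. At stake is whether the stated attrition margin and the stated power describe the trial that will be analysed.

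**Working it through.** **Inputs, all from section 7.1 unless noted.** dz = 0.77; alpha = 0.05; target power 0.8; required n = 16; dropout 25%; recruits 20; quoted power 0.9 at N = 20. The one-tailed direction comes from section 7.2.

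**Power formula.** For a paired t-test with n completers, the noncentrality is δ = dz × √n on n − 1 degrees of freedom. Two-tailed power is P(T > t(0.975)) + P(T < −t(0.975)), and one-tailed power is P(T > t(0.95)), with T noncentral t.

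- n = 20: δ = 0.77 × √20 = 3.44
- n = 16: δ = 0.77 × √16 = 3.08
- n = 15: δ = 0.77 × √15 = 2.98

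| Completers | Two-tailed 0.05 | One-tailed 0.05 |
|---|---|---|
| 20 | 0.904 | 0.953 |
| 16 | 0.821 | 0.902 |
| 15 | 0.792 | 0.883 |

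**Reproducing the plan.** Two-tailed, 16 is the smallest n with at least 80% power (15 gives 0.792), and N = 20 gives 0.904. Both published figures, n = 16 and 0.9, come out. One-tailed, 80% power needs only 12 (0.803), and N = 20 gives 0.953. The plan's figures are therefore two-tailed, with every subject counted as analysed.

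**Dropout.**

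- Route to the plan's 20: 16 × (1 + 0.25) = 20.
- Recruits needed for 16 completers at 25% loss: 16 / (1 − 0.25) = 21.3, rounded up to 22.
- Completers from 20 at 25% loss: 20 × 0.75 = 15.
- Largest loss that still leaves 16 of 20: (20 − 16) / 20 = 20%, or 4 subjects.

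**Size of the gap.** The shortfall is one completer (15 against 16), or two recruits (20 against 22). Two-tailed power at 15 is 0.8 of a percentage point below target (0.792 against 0.80) and about 11 points below the figure for full completion (0.904 − 0.792 = 0.112). One-tailed power at 15 is 0.883, about 8 points above the 0.80 target.

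**The case against.** **The 25% may be a top-up.** The phrase can be read as adding a quarter of 16, four spare subjects, which gives exactly 20. That explains where the number came from, but the text calls the 25% a dropout risk. On the top-up reading the sentence still claims a tolerance that 20 recruits do not give; they tolerate 20%. The need to reword stands either way.

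**The two sentences are not in conflict.** A reader might infer that the dropout sentence and the 0.9 sentence cannot both be true. The documents do not support that. The second is a conditional statement about N = 20 with other inputs fixed. It does not claim 0.9 after attrition, and giving the power at full enrolment beside a minimum n is ordinary practice. What it lacks is the condition that all 20 are analysed.

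**The trial is not shown to be underpowered.** A reader might also infer that dropout takes power below both 0.8 and 0.9. Against 0.8 that is true only two-tailed, and then by less than one point. Under the one-tailed test that section 7.2 plans, 15 completers give 0.883.

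**Fifteen is a worst case for objective 1.** Someone lost in the second home trial has already supplied SRT data. The plan does not say whether the 25% covers the whole study or only the time up to the speech tests. The count of 15 applies to the primary endpoint only if all of the loss comes before the second lab session. This objection stands, and the wording of the fix should reflect it.

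**Conclusion.** The attrition tolerance in section 7.1 is wrong as written: 20 recruits support 16 completers at up to 20% loss, not 25%. The 0.9 is correct as a two-tailed power for 20 analysed subjects but is given without that condition. Severity is minor. At the stated 25%, all lost before the speech tests, the plan ends one completer short of its own n, with power 0.79 two-tailed or 0.88 one-tailed. On the plan's dz, objective 1 is not materially underpowered.

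These figures rest on dz = 0.77 and on dropouts contributing nothing to the paired test. They would change if the inputs of section 7.1 were revised, because dz = 0.77 equals 1/1.3 and does not use the stated correlation of 0.8. With that correlation, the SD of the difference is 1.3 × √(2 × (1 − 0.8)) = 0.82 dB and dz is about 1.22. At that dz, 15 completers give power of about 0.99 two-tailed and above 0.99 one-tailed. The choice of dz and the unstated sidedness are separate matters. They affect the power figures but not the dropout arithmetic.

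**What to change.** Reword two sentences in section 7.1 and leave N at 20:

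- State that 20 recruits allow for up to 20% dropout (4 subjects) before the speech tests at the second lab session, leaving 16 completers.
- State that 0.90 is the two-tailed power if all 20 are analysed, and give the power at 15 completers (25% lost before the speech tests) with its sidedness: 0.79 two-tailed, 0.88 with the one-tailed test of section 7.2.

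If dz or the sidedness in section 7.1 is corrected, recompute these figures at the same time so that the paragraph is rewritten only once.

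The cost is a small text amendment and a slightly less favourable stated margin. It needs no extra subjects and no change to design or analysis. Raising recruitment to 22 would be the alternative if the sponsor wants to keep the 25% claim for 16 completers, but the power figures above do not call for it.
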